## **1. PROJECT TITLE**

Study #: 161983

Perinatal Precision Medicine (NSIGHT2): A randomized, blinded, prospective study of the clinical utility of rapid genomic sequencing for infants in the acute-care setting

## **4. ESTIMATED DURATION OF THE STUDY**

Enrollment in Rady Children's Hospital acute care settings to begin in 2017 and to continue through 2019, with follow-up including chart review of outcomes through 2025.

## **5. LAY LANGUAGE SUMMARY OR SYNOPSIS (no more than one paragraph)**

This study will seek to determine if rapid genomic sequencing improves outcomes for acutely ill infants. We will enroll up to 1,000 acutely ill infants in a prospective, randomized, blinded study to either rapid Whole Genome Sequencing (WGS) or rapid Whole Exome Sequencing (WES, which is 2% of the genome and ~2-fold less expensive). Outcomes will be measured both by objective clinical measures and family perceptions (patient/family centered outcomes). Primary analysis of WGS or WES will be in infants alone. Secondary analysis, in infants who do not receive a diagnosis, will be of families – ideally trios (mother, father and affected infant), which is ~2-fold more expensive. Trios will be analyzed within the same randomization arm (WGS or WES). This study is designed to quantify which acutely ill infants benefit from rapid genomic sequencing, by how much they benefit, how they benefit, which rapid genomic sequencing method is superior, and the cost effectiveness of such testing.

## **6. SPECIFIC AIMS**

**Specific Aim 1.** Determine if, and by how, much rapid WGS is associated with better outcomes than rapid WES in acutely ill infants. The null hypothesis is that both tests are equivalent. This may occur, for example, if the diagnosis rate is similar or the additional diagnoses from WGS do not alter clinical management.

**Specific Aim 2.** Determine if and by how much rapid WGS is associated with better perceived outcomes in parents of acutely ill infants than rapid WES in acutely ill infants. The null hypothesis is that both tests are

equivalent. In addition, this will be the first study to examine the family-centered outcomes of rapid genomic sequencing, and particularly in Hispanic/Latino families.

**Specific Aim 3.** To compare diagnostic rates, time to diagnosis, and outcomes of rapid genome-wide sequencing compared with historical matched cases who received standard care before genome-wide sequencing was available. The null hypothesis is that genome wide sequencing does not increase diagnosis rate, time to diagnosis or outcomes.

**Specific Aim 4.** To compare diagnostic rates of singleton analysis versus familial analysis (ideally trio) and the cost-effectiveness of each testing method (rapid singleton WGS, rapid singleton WES, rapid trio WGS and rapid trio WES). The null hypothesis is that adding familial sequencing data does not significantly increase diagnostic yield.

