The incidence of genetic diseases in acutely ill infants receiving NICU and PICU care is unknown since no large scale genomic sequencing study has been performed in this population. While genetic diseases are known to be a leading cause of death among infants, the impact of timely diagnosis in acutely ill infants on clinical care of these diseases is unknown. We propose a prospective, randomized study to compare outcomes in up to 1,000 acutely ill babies, all of whom will receive some form of genomic sequencing. We will use genomic

sequencing to prospectively test the hypothesis that rapid WGS confers significantly better outcomes to a subset of ill neonates/infants and their families than rapid WES or current clinical practice (clinical diagnosis and standard diagnostic tests). Molecular diagnostic yield, time to diagnosis and changes in management will be secondary outcomes.

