## 9. RESEARCH DESIGN AND METHODS

### Summary of design

A prospective, randomized, controlled, blinded trial to evaluate the comparative outcomes and effectiveness (clinical utility, perceived family utility, and cost effectiveness) of two methods of rapid genomic sequencing (WGS and WES) and two methods of analysis (singleton probands and familial trios) in acutely ill infants. Enrollment in this study includes enrollment into a Newborn/Infant biorepository and co-enrollment into the Genomic Biorepository: Protocol for the Collection, Storage, Analysis, and Distribution of Biological Samples, Genomic and Clinical Data (IRB #160468). Historic controls will be obtained from a separate retrospective chart review study following IRB approval.

Acutely ill infant inpatients who have an undiagnosed illness, and their families, will be eligible to participate in the study. We will enroll up to 1,000 infants. Locally, the study population will be recruited from Rady Children's Hospital (RCH) inpatient population, primarily the NICU, PICU and cardiovascular intensive care unit (CVICU), with a smaller population presenting to other hospital in-patient services. Recruitment will be targeted at the RCH main campus, but it may include referrals from satellite locations in the RCH network (particularly the RCH NICU network throughout San Diego County). All patients will continue to receive routine care as clinically indicated, including the state NBS and other genetic testing as determined by their treating providers. Half of the affected study participants will be randomized to receive rapid WGS and the other half will receive rapid WES. Each arm will initially be analyzed using the patient's (proband's) sample only. If a proband-only analysis fails to yield a diagnosis, genomic data from the biological family members (typically parents), when available, will be used to supplement analysis (trio analysis). Occasionally, a second affected sibling may be available for family analysis. Not infrequently, the father is not available for study. Similarly, we anticipate the need for targeted genetic analysis of biological parents, and possibly other family members, to confirm diagnostic results and/or provide additional information regarding inheritance.

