#### Stage Two Analysis:

If a diagnosis is not found promptly (within 24 hours) via a singleton analysis, the family (or any combination of parents and/or other family members) will be analyzed using the same technology that the patient was randomized to receive. Dependent upon logistics and the acuity of the patient's illness, we may generate trio genomic sequences simultaneously or in stages (singleton then parental duo).

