### **Sample size determination**

Preliminary results indicate that rapid trio WGS will result in a change in clinical utility index (CUI) ~50% of cases (a key secondary outcome). We propose that WES must yield a CUI of 40% or lower to justify the cost differential between WGS and WES. Using  $\alpha=0.05$ , we can achieve a power of 80% with 325 patient per arm, well below our proposed 500 patients per arm. Preliminary results indicate that rapid trio WGS is associated with 2.9 QALYs saved per infant tested (a key primary outcome). No similar analysis has been performed for WES. Additional patients, therefore, increase our power to assess differences in outcomes, and also compensates for technical or other issues that may cause some sample to be unanalyzable. Notably, we have proposed multiple measures of outcomes and clinical utility in addition to QALYs and CUI, respectively, and our power calculations do not correct for multiple testing. We feel this is acceptable for two reasons: First, these outcome variables are not completely independent making a Bonferroni correction overly conservative. Second, as there is little preexisting data on this subject, we felt a less conservative approach often utilized in preliminary studies is appropriate.

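### Do the null hypotheses in Specific Aims 1, 2 and 4 let a non-significant result be reported as no effect?

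*Combined protocol and SAP*

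**What the plan says.** Section 6 sets out four aims. Aims 1 and 2 ask whether, and by how much, rapid WGS does better than rapid WES, first on outcomes and then on outcomes as parents perceive them. The Aim 1 null reads "The null hypothesis is that both tests are equivalent. This may occur, for example, if the diagnosis rate is similar". The sentence does not stop there: it adds a second route to the null, that the extra WGS diagnoses lead to no change in care. Aim 2 uses the same word, equivalent, without the illustration.

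Aim 3 (against historical controls) has a plain null of no increase. Aim 4 (singleton against family analysis) has the null that "The null hypothesis is that adding familial sequencing data does not significantly increase diagnostic yield".

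Elsewhere the stated purpose is superiority. Section 5 wants to learn "which rapid genomic sequencing method is superior", and Section 7 tests whether "rapid WGS confers significantly better outcomes". The sample size paragraph in Section 10 takes about 50% for WGS on the clinical utility index (CUI) and says "We propose that WES must yield a CUI of 40% or lower to justify the cost differential between WGS and WES". It concludes that "we can achieve a power of 80% with 325 patient per arm, well below our proposed 500 patients per arm".

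**The concern.** In a superiority test the null is no difference, and failing to reject it does not show that two tests are equivalent. Calling the null equivalent, with no margin, invites that misreading. Aim 4 goes further. Because its null contains the word *significantly*, a non-significant result satisfies it by definition, even when some infants gained a diagnosis.

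The stakes are practical. WES and singleton analysis are the cheaper options, so readers will ask whether they are good enough. A non-significant result reported as equivalence could support the cheaper option while the confidence interval still includes the 10-point CUI gap that the protocol ties to the cost of WGS.

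**Working it through.** **1. Is a margin missing?** The plan's own sample size shows which test is meant. Inputs from Section 10: 50% against 40%, alpha 0.05, power 80%. The standard formula against zero difference, with pooled rate 0.45, is

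n = [z(alpha) × sqrt(2 × 0.45 × 0.55) + z(power) × sqrt(0.5 × 0.5 + 0.4 × 0.6)]² / 0.10².

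With one-sided alpha (z = 1.645) and z(power) = 0.842 this is (1.157 + 0.589)² / 0.01 = 305. The continuity correction, n/4 × [1 + sqrt(1 + 4/(n × 0.10))]², gives 325, the stated figure. So 325 per arm comes from a test of no difference, with 10 points as the alternative. Such a null needs no margin.

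**2. What does equivalent mean in Aim 1?** The sentence after it gives two ways in which the null could hold: similar diagnosis rates, or extra diagnoses that change nothing in care. Both are states of the world. Neither tells an analyst how to read a p-value. In this context equivalent means no difference.

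**3. Would rewording change any CUI result?** At a true 50% against 40%, exact enumeration with Newcombe intervals gives the probability that the 95% CI includes both zero and 10 points.

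| Per arm | 95% CI includes 0 | 95% CI includes 0 and 10 points |
|---|---|---|
| 325 | 26% | 24% |
| 500 | 11% | 8% |

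The first column is ordinary type II error for a two-sided test; the second adds a condition on the upper limit. Both depend only on the rates, the numbers and the test. They are the same whether the null is written as equivalent or as no difference.

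**4. When would Aim 4's wording matter?** Family analysis is used in two situations: "If a proband-only analysis fails to yield a diagnosis, genomic data from the biological family members", and "If a diagnosis is not found promptly (within 24 hours) via a singleton analysis". Apart from a diagnosis withdrawn at confirmation, infants can gain a diagnosis at stage two but not lose one. The plan names no test. Assume an exact paired (McNemar) test with all b discordant pairs in one direction, so that two-sided p = 2 × 0.5^b:

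- b = 5: p = 0.0625
- b = 6: p = 0.031

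Five added diagnoses among 500 infants is a gain of 1.0 point (exact 95% CI 0.3 to 2.3) and would meet the null as worded. With b binomial on 500 infants, the chance of one to five added diagnoses is:

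| True gain | P(1 to 5 added) |
|---|---|
| 1 point | 61% |
| 2 points | 6.5% |
| 3 points | 0.25% |

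Deleting *significantly* changes none of these p-values, intervals or probabilities. It changes only whether the null is said to be met or said not to be rejected.

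**The case for a change.** The best argument for a correction is that it costs almost no effort and Aim 4 cannot be excused as loose phrasing. Aim 3, just before it, already has the right form. The protocol measures many outcomes without multiplicity correction, so some non-significant results are likely and need a safe reading. Enrolment may also fall short. Section 10 expects about 250 infants by September 2019; if that means 125 per arm, the chance that the 95% CI covers both zero and 10 points at a true 10-point CUI gap is about 62%.

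The remark on Aim 4 stands: a hypothesis should describe the yield, not the result of a test. The rest does not carry over into a change. The 62%, like the 8% and 24%, measures limited power, which no choice of words improves. It also concerns the CUI, which Section 10 calls a key secondary outcome. Reporting the size of the difference is already an objective of Aims 1 and 2. If the plan says too little about confidence intervals, that is a gap in analysis detail and not a fault in the nulls. Setting a CI beside the 10-point planning figure could even create an informal margin where the design has none.

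**Conclusion.** The plan needs no change. For Aims 1 and 2, equivalent is loose wording for no difference in a superiority design; no margin is missing, and no equivalence conclusion is planned. For Aim 4, *significantly* is a clerical slip. A competent analyst will test for an increase in yield and report the added diagnoses with an interval whichever way the sentence reads.

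The slip could mislead only if family data added very few diagnoses, about five or fewer in 500. That rests on the assumed exact paired test and an assumed true gain near 1 point. Section 7 points to a larger gain: de novo variants were the leading mechanism in the sponsor's earlier series, and it describes them as much harder to find by singleton than by trio testing.

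This conclusion would change if the sponsor intended to claim that WES or singleton analysis is as good as the dearer option. That claim would need a margin and its own test, and nothing in the document announces it.

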## 7. BACKGROUND AND SIGNIFICANCE

15% of the 4 million infants born in the US each year are admitted to a Neonatal Intensive Care Unit (NICU) or Pediatric Intensive Care Unit (PICU) for diagnosis and treatment of an acute illness. Approximately 6% of infants born in San Diego county are admitted to the RCHSD Level IV NICU or regional PICU. Genetic diseases are common among infants in ICUs, although precise prevalence data does not exist. There are more than 8,000 defined genetic diseases. Malformations and genetic disorders are the leading cause of infant mortality, NICU mortality and PICU mortality in the US. One study in a large children's hospital reported that 51% of infant deaths were from a malformation and/or a genetic disorder. 19% of deaths in the PICU of a large children's hospital were due to genetic diseases. Our experience suggests that up to 40% of level IV NICU infants may benefit from rapid WGS for genetic disease diagnosis. However, studies to date have been limited to a small proportion of NICU admissions, and may therefore be subject to ascertainment bias.

Newborn Screening (NBS), although variable by state, identifies 44 diseases within several weeks of birth, primarily inborn errors of metabolism (IEM) that collectively affect 0.3% of newborns. Typically, these diseases are asymptomatic at birth. NBS is not designed to diagnose genetic conditions in acutely ill infants, but rather to screen the population. However, IEMs are detected in 1.5% of NICU infants, and are associated with ~20% mortality. Rapid diagnosis of IEMs by NBS allows timely institution of treatment that saves thousands of Quality Adjusted Life Years (QALY) and Disability Adjusted Life Years (DALY) per year. The QALY is a generic measure of disease burden, including both the quality and the quantity of life lived. It is used in economic evaluation to assess the value of medical interventions. One QALY equates to one year in perfect health. Likewise, the DALY is a measure of overall disease burden, expressed as the number of years lost due to ill-health, disability or early death. IEMs represent the tip of the genetic disease iceberg in NICU and PICU infants, but it is not known whether broad use of genomic sequencing in such infants would save additional QALYs and DALYs.

Other than IEMs and common chromosomal diseases (e.g. Down syndrome and 22q11 microdeletion syndrome), ascertainment rates of genetic diseases in NICUs and PICUs are low. Serial, single gene sequencing is the current standard for molecular diagnosis of genetic diseases for acutely ill infants. However, it is usually too slow for clinical utility in these sick infants as time-to-result for each test is >4 weeks, and more typically 6 - 26 weeks. Sequential testing may take years. Rapid WGS and WES allow simultaneous testing of most of the 8,000 known genetic disorders within 1 week.

Due to lack of methods for rapid molecular diagnosis, NICU and PICU treatment of genetic diseases is usually empiric. We recently invented WGS with time-to-result of ~26 hours, providing a method for timely diagnosis in acutely ill infants. In the only published study of rapid WGS (with our prior 2-day protocol), we found that

20 (57%) of 35 enrolled infants received a diagnosis by rapid trio WGS, in contrast to 9% using all conventional testing methods. Acute clinical usefulness was noted in 13 (65%) of 20 infants with a rapid WGS diagnosis, four (20%) had diagnoses with strongly favorable effects on management, and six (30%) started palliative care. However, ascertainment of eligible infants was delayed, and the median diagnosis was at day of life ~50. This impacted the effect of diagnosis on outcomes since 100-day mortality was 57% (12 of 21) in infants with a genetic diagnosis. This was not a randomized controlled study, infants were selected based on likelihood of having an actionable genetic diagnosis, and all infants received both WGS and conventional tests. Thus, this study was not designed to determine the maximum improvement in outcomes achievable nor the proportion of NICU infants who benefit. The diagnostic variants affected coding regions of genes, and therefore would potentially have been detected by WES (rather than WGS). The most common mechanism was de novo mutation causing dominant disorders, which are much more difficult to identify by singleton than trio testing.

Recently we implemented rapid (3 days) trio WGS at RCIGM. For 4 months we have enrolled acutely ill infants at RCHSD in the protocol “Genomic Biorepository: Protocol for the Collection, Storage, Analysis, and Distribution of Biological Samples, Genomic and Clinical Data (IRB #160468)”. Among 35 families with acutely infants nominated, 29 (83%) were enrolled. The fastest time to diagnosis was 41 hours from blood draw to communication of provisional diagnosis. On average, diagnosis occurred within one week. At time of submission, WGS had been interpreted in 29 families with 30 symptomatic infants, yielding informative data in 28. 15 (53%) of infants received diagnoses. In 14 (50%), the initial diagnosis was by rapid trio WGS. 13 patients had single nucleotide variants and two had structural variants. The leading mechanism of disease was de novo mutations causing dominant genetic disorders. Only two patients received diagnoses prior to completion of rapid trio WGS. Following diagnosis by rapid trio WGS, clinical management changed in 12 (43% of infants tested). Of these, medications were changed in 9 (32%) infants; One infant avoided needless major surgery; Palliative care was initiated in two infants with > \$6M potential healthcare savings. This data replicated our published previous experience at Children’s Mercy Hospital in Kansas City, but was remarkable since enrollment was much broader at RCHSD (namely, the 4 or 5 infants with greatest need of a definitive diagnosis each week).

Additionally, we recently concluded the first randomized, controlled, partially blinded, prospective trial of the 28-day diagnostic yield of rapid trio WGS plus conventional testing versus conventional testing in acutely ill NICU infants (the NIH-funded “NSIGHT” study). While the results are still being evaluated, we found that patients in the control arm of the study also received genetic diagnoses through next-generation sequencing, including WES and WGS, upon unblinding of neonatologists. Similarly, we observed a cross-over rate for compassionate use of WGS of 10%. Nevertheless, we found that the 28-day rate of diagnosis was 5 of 33 (15%) in the control arm and 14 of 32 in the rapid trio WGS arm (44%,  $p < 0.01$ ). Thus, provisionally, we conclude that rapid trio WGS has greater 28-day diagnostic yield than conventional testing. This study was not designed to evaluate clinical utility.

Finally, a group that we are collaborating with in Melbourne Australia published a study of 80 children  $< 2$  years of age with likely genetic diseases. Singleton WES yielded a 58% rate of diagnosis. WES is four-fold less expensive than WGS, and singleton testing is 2-fold less expensive than trios. Their enrollment criteria favored children with a positive family history, which enriched for infants with recessive diseases (which are readily identified by singleton testing). While de novo mutations were the leading cause of diagnosis in their study, recessive diseases were much more common in their cohort than other studies. They utilized WES at standard speed (~6 month time to diagnosis), and thus their study was not well designed to assess clinical utility.

These studies, which comprise the literature to date, demonstrate that rapid WGS significantly increases the rate of diagnosis and time to diagnosis compared with traditional testing. As yet, however, no randomized

controlled study has compared the rate of diagnosis of WGS and less costly WES, nor of trio versus less costly singleton testing. It is no longer acceptable to have randomization to a control arm that delays reporting of results up to 12 weeks (such as routine speed WGS or WES). Furthermore, although data from studies to date shows clinical utility of WGS or WES, it is not yet clear what the specific indications for such testing should be in acutely ill infants, nor whether WGS or WES are associated with improved outcomes. Furthermore, both the cost of WGS and WES, and their clinical utility, increase as time to result decreases. The optimal match of timeliness and cost effectiveness are not yet known. Finally, it is not clear whether patient and family perceptions of improved outcomes match those of physicians. Therefore, we propose to examine standard and family-centered outcomes in acutely ill infants receiving rapid WGS or rapid WES as a first-line test.

Little data exists on the clinical utility of rapid genomic sequencing for cost-effectiveness modeling of interventions initiated in the early days to weeks of life. Studies have shown that NBS decreases morbidity and mortality because it provides rapid screening at birth for diseases that benefit from early treatment. Additionally, rapid genomic diagnosis of critically ill babies may diagnose lethal disorders, enabling initiation of palliative care, potentially decreasing physical suffering to the infant, and prioritizing bonding with family members rather than futile heroic interventions. Studying the clinical impact of WGS or WES for acutely ill infants compared with historic controls will provide information on the incidence of genetic disease in this population and help determine how WGS and WES benefit acutely ill infants, their families and their clinical care providers. Likewise, we will attempt to aggregate data for QALYs and DALYs to analyze the clinical utility of genomic sequencing, in addition to clinician surveys of utility, and to assess economic impact of testing over the lifetime of each patient.

Rapid WES is ~2-fold less expensive than rapid WGS but has at least one additional day of time to results. There is no data comparing the diagnostic or clinical utility of WES and WGS. WES is the only genome wide sequencing test routinely covered by insurers. In addition, as noted above, all of our rapid WGS cases could theoretically have been detected by WES. Conversely, although WES can analyze the coding regions of nearly all potentially disease causing genes, we believe that WGS is superior, despite its higher costs, due to its ability to detect de novo variants, structural variants (SV), and to interrogate regions of extreme GC content. WGS provides coverage of non-coding variants that can be clinically identified as definitely disease causing. As such, we believe an analysis of diagnostic rates between the two types of tests will show that WGS does in fact provide more diagnoses than WES. However, such increases in diagnoses may not lead to an increase in changes in care as the variants that can be detected only by WGS may be less amenable to specific therapeutic interventions. The primary goal of this study is to evaluate which method provides the optimal outcomes in acutely ill infants with likely genetic diseases. However, we anticipate that we may also – in subsequent amendments – retrospectively re-analyze these samples to determine if WGS or WES has superior ability to yield pharmacogenomic and secondary findings related to childhood-onset conditions. In subsequent amendments, families may potentially be asked for their opinions on receiving such additional testing results, if available, following the discharge of their child. As pharmacogenomics knowledge grows, the need for informed drug choice and dose will be crucial in effectively managing critically ill patients and preventing secondary harm. In particular, we anticipate a future amendment to examine the prevalence of the genetic predisposition to hearing loss following the administration of aminoglycosides, an antibiotic very commonly used in NICUs.

The incidence of genetic diseases in acutely ill infants receiving NICU and PICU care is unknown since no large scale genomic sequencing study has been performed in this population. While genetic diseases are known to be a leading cause of death among infants, the impact of timely diagnosis in acutely ill infants on clinical care of these diseases is unknown. We propose a prospective, randomized study to compare outcomes in up to 1,000 acutely ill babies, all of whom will receive some form of genomic sequencing. We will use genomic

sequencing to prospectively test the hypothesis that rapid WGS confers significantly better outcomes to a subset of ill neonates/infants and their families than rapid WES or current clinical practice (clinical diagnosis and standard diagnostic tests). Molecular diagnostic yield, time to diagnosis and changes in management will be secondary outcomes.

